### *Eligibility criteria*

#### Inclusion criteria

- patients  $\geq$  45 years undergoing in-hospital major non-cardiac surgery
  - major orthopedic surgery
    - hip surgery
- undergoing emergent or urgent surgery (i.e. emergent or urgent visitation to the Department of Orthopedic Surgery)
- fulfil 1 or more of the following 4 inclusion criteria, which are all determined during the conversation with the patient:
  1. Ischemic heart disease, defined by any of the following criteria
    - A. angina pectoris

- B. prior myocardial infarction
- C. prior percutaneous coronary intervention
- D. prior coronary artery bypass graft

2. Peripheral arterial disease, defined by any of the following criteria

- A. intermittent claudication
- B. reduced peripheral arterial blood flow
- C. prior vascular surgery due to peripheral arterial disease

3. Prior stroke

OR

4. any 1 of 7 risk criteria

- A. age  $\geq 70$  years;
- B. congestive heart failure
- C. prior transient ischemic attack;
- D. diabetes and currently taking an oral hypoglycemic agent or insulin
- E. hypertension
- G. preoperative serum creatinine  $>175 \mu\text{mol/L}$  ( $>2.0 \text{ mg/dl}$ )
- H. smoking within 2 years of surgery

Exclusion criteria

- History of peripheral arterial disease affecting both upper limbs
- Renal failure with  $\text{eGFR} < 30 \text{ ml/min/1.73m}^2$
- Cardiogenic shock or cardiac arrest during the current hospital admission
- Reoperation after elective surgery carried out during the current hospital admission
- Other conditions that prevent the performance of remote ischemic preconditioning.
- Not capable of giving informed consent after oral and written information
- Previously included in this trial

*Interventions*

Remote ischemic preconditioning: 4 cycles of forearm ischemia (200 mmHg, 5 min) and reperfusion (5 min) immediately after induction of anesthesia. The procedure should be performed on the limb opposite the one used for iv infusions. For patients with systolic blood

pressures >185 mmHg, the cuff will be inflated to at least 15 mmHg above the patient's systolic blood pressure.

*Primary outcome*

- Number of patients with peak plasma cardiac troponin I (cTnI)  $\geq$  45ng/L (99th percentile URL, 10% CV at 40ng/L) during surgery or during the first 4 days after surgery (perioperative myocardial injury). If elevated at baseline (preoperative) a 20% or greater increase of cTnI according to baseline is required for the diagnosis of a perioperative myocardial injury [15].
  - o Holstebro Hospital: Number of patients with peak plasma cardiac troponin I (cTnI) > 24 ng/L (99th percentile URL, 14% CV)

*Secondary outcome*

- Peak plasma cTnI and total cTnI release (area under the curve) during surgery or during the first 4 days after surgery
- Plasma N-terminal Pro-Brain Natriuretic Peptide (NT-proBNP) before surgery and at day 1 after surgery.
- Endothelial dysfunction assessed by the non-invasive EndoPat system (24 hours after surgery, only done at Zealand University Hospital)
- Biomarkers of coagulation (only patients included at Holstebro Hospital)
- Perioperative myocardial infarction (Universal definition of myocardial infarction, published in 2012 [15])
  - A typical rise or fall of cTnI with peak plasma cTnI  $\geq$  45ng/L (99th percentile URL, 10% CV at 40 ng/L) (Holstebro cTnI > 24 ng/L), and with at least one of the following:
    - Symptoms of ischemia

---

 Defined as a preoperative cTnI  $\geq$  45ng/L (99th percentile URL, 10% CV at 40ng/L)

- New or presumed new significant ST-segment-T wave (ST-T) changes or new left bundle branch block (LBBB)
  - Development of pathologic Q waves in the ECG
  - Imaging evidence of new loss of viable myocardium or new regional wall motion abnormality
  - Identification of an intracoronary thrombus by angiography or autopsy
- Cardiac death with symptoms suggestive of myocardial ischemia and presumed new ischemic ECG changes or new LBBB, but death occurred before cardiac biomarkers were obtained, or before cardiac biomarker values would be increased.
  - Development of new pathologic Q waves on an ECG or pathological findings of a healing myocardial infarction if troponin levels were obtained at times that could have missed the clinical event
- Major adverse cardiovascular events (30 days, one year and five years after surgery)
    - Nonfatal cardiac arrest, coronary revascularization procedure (PCI or CABG), acute coronary syndrome, stroke, congestive heart failure, new clinically important cardiac arrhythmia, peripheral arterial thrombosis, rehospitalization for cardiovascular reasons.
  - Length of postoperative hospital stay
  - Length of intensive care unit stay
  - All-cause mortality (30 days, one year and five years after surgery)
    - cardiovascular or non-cardiovascular (a clearly documented non-cardiovascular cause)

Besides the inclusion and exclusion criteria, the following baseline data and preoperative/postoperative risk factors will be collected from each patient (records):

- Age, sex

- co-morbidities: chronic obstructive pulmonary disease, atrial fibrillation, active cancer, autoimmune diseases
- medications (Paracetamol, NSAID, steroid, antibiotics, opioid, ASA, statin, brilique, clopidogrel, anticoagulant medications,  $\beta$ -blocker, calcium antagonist, diuretics, ACE-I, angiotensin antagonist, antiarytmic, nitrate, digoxin, antidiabetics incl. insulin) preoperative and during hospitalization
- preoperative ASA score
- preoperative revised cardiac risk index score
- type and length of surgery
- type and length of anesthesia and type of analgesia
- Intraoperative hypotension (and length) defined as a systolic blood pressure <100mmHg
- Preoperative and postoperative plasma creatinine (incl. eGFR) and plasma hemoglobin
- blood transfusion
- Clinical events during hospitalization according to the Clavien Dindo classification [16, 17] e.g. pneumonia, sepsis, acute respiratory failure, acute kidney failure and lung embolism.

The one and five year follow-up on all included patients will be performed with information (procedure- and diagnosis codes) registered in the Danish National Patients Register (Landspatientsregisteret). Likewise, information on death and cause of death will be deducted from "Dødsårsagsregisteret".

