#### *Participant timeline*

*Intervention:* The remote ischemic preconditioning procedure is carried out immediately after the induction of regional or general anesthesia. The blood pressure cuff is placed on the upper limb. The cuff is inflated to 200 mmHg resulting in a total occlusion of the blood flow to the limb. After 5 minutes of ischemia the cuff is deflated and the limb is reperfused for 5 minutes. The procedure is carried out 4 times in a row. For patients with systolic blood pressures >185 mmHg, the cuff will be inflated to at least 15 mmHg above the patient's systolic blood pressure. The first round should be completed before the initiation of surgery.

The patients will have blood collected to assess cTnI (preoperative and in the morning at days 1, 2, 3 and 4 after surgery) and NT proBNP (preoperative and in the morning at day 1 after surgery). All patients with a cTnI assessment  $\geq 45\text{ng/L}$  will have a minimum of one ECG performed and a medical doctor will evaluate the patient for the presence of an ischemic or non-ischemic event that can explain the elevated cTnI (i.e. sepsis, pulmonary embolism, cardioversion). The medical doctor will determine whether further action should be taken. If necessary, a cardiologist will be consulted. Patient included at Holstebro Hospital will have blood collected for assessment of coagulation biomarkers. The blood samples are taken preoperatively, 2 hours after incision and in the morning at day 1 and 2 after surgery (4 times 6 ml blood).

The investigator observes the patients during their stay in hospital and records the occurrence of any primary or secondary outcomes. The investigator will undertake a short- and long-term follow up (30 days, one and five years after surgery) and record the occurrence of any primary or secondary outcomes. The follow-up will be carried out by reviewing the patients' electronic hospital records, by a personal phone call and with data from the Danish National Patient Register and "Dødsårsagsregisteret".

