### Plasma cardiac troponin I

Plasma cTnI will be analyzed at the local department of biochemistry using Siemens Healthcare Dimension Vista (Zealand University Hospital, Herlev Hospital), Abbott high-sensitive troponin I (Holstebro Hospital).

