### *Statistics*

All statistical analysis will be done with SPSS/PC+ package (SSPS, Chicago, IL, USA) or the SAS 9.3 package. Data will be analyzed using non-parametric or parametric statistics depending on the distribution of data. Differences are considered significant when  $p < 0.05$ . We will do a per-protocol analysis and an intention-to-treat analysis.

A medical doctor will evaluate all patients with a rise in cTnI  $\geq 45\text{ng/L}$  in order to determine whether the elevation in cTnI is due to an ischemic or non-ischemic disease. In the final data analysis, we will do an analysis, which includes all patients (ischemic and non-ischemic) and a second analysis, which will only include patients with an ischemic disease.

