**The primary analysis**

Comparing the incidence of myocardial injury (No. (%)) in the intervention group versus the control group. We plan to use a chi-square test. The difference is considered to be significant if the two-sided p-value < 0.05.

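### Holstebro's injury cut-off is >24 ng/L, but elevation at baseline is defined only as ≥45 ng/L, so the 20% rise rule misses unchanged preoperative values between the two

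*Combined protocol and SAP*

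**What the plan says.** In the current protocol, under Primary outcome, the event at Zealand and Herlev is a peak cTnI of at least 45 ng/L during surgery or the following four days. For patients already elevated before surgery, "a 20% or greater increase of cTnI according to baseline is required for the diagnosis of a perioperative myocardial injury". Footnote 1 gives the meaning of elevated at baseline: "Defined as a preoperative cTnI $\geq$ 45ng/L (99 th percentile URL, 10% CV at 40ng/L".

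A sub-bullet then sets a different event for one site: "Holstebro Hospital: Number of patients with peak plasma cardiac troponin I (cTnI) > 24 ng/L". It mentions neither a baseline rule nor a time window. The infarction criterion under Secondary outcome was adapted for that site: "Holstebro cTnI > 24 ng/L), and with at least one of the following". Footnote 1 was not.

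The site difference comes from the assay, as the section on plasma cardiac troponin I states: "Siemens Healthcare Dimension Vista (Zealand University Hospital, Herlev Hospital), Abbott high-sensitive troponin I (Holstebro Hospital". Troponin is sampled "preoperative and in the morning at days 1, 2, 3 and 4 after surgery" (Participant timeline).

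The final SAP's primary analysis describes the outcome only as "Comparing the incidence of myocardial injury (No. (%)) in the intervention group versus the control group". It defines neither injury nor elevation at baseline. Neither amendment log gives a Holstebro baseline threshold.

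**The concern.** The 20% rule exists so that a troponin already raised before surgery is not counted as perioperative injury. It works only if the threshold for elevated at baseline matches the threshold for an event. At Zealand and Herlev both are 45 ng/L. At Holstebro the event threshold was lowered to >24 ng/L and the baseline threshold stayed at 45, which leaves a gap for preoperative values above 24 and below 45 ng/L.

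Two things are at stake. First, a patient in the gap can become a primary event without any perioperative change, and preconditioning cannot be expected to prevent an elevation that was there beforehand. Such events dilute the contrast between arms. Second, the text supports more than one coding of the primary outcome at one site, and the SAP does not choose between them.

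**Working it through.** **Step 1. Apply the rule as written.** A Holstebro patient is an event if the peak is >24 ng/L and, only when baseline is ≥45 ng/L, the peak is at least 1.2 × baseline. The aligned rule asks for the 20% rise whenever baseline is >24 ng/L. The Vista rule uses 45 ng/L for both thresholds.

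| Baseline → peak (ng/L) | Holstebro, as written | Holstebro, aligned | Vista sites |
|---|---|---|---|
| 30 → 30 | event | no event | no event |
| 30 → 36 | event | event | no event |
| 44 → 39.6 | event | no event | no event |
| 44 → 44 | event | no event | no event |
| 45 → 45 | no event | no event | no event |
| 50 → 50 | no event | no event | no event |
| 50 → 60 | event | event | event |

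As written, an unchanged 44 counts and an unchanged 45 does not. Even a fall from 44 to 39.6 counts.

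**Step 2. List the possible readings.** (a) The sub-bullet inherits the 20% rule with footnote 1 as printed: unchanged 30 is an event, unchanged 50 is not. (b) The sub-bullet stands alone with no baseline rule: both are events. (c) Elevated means above the site's own 99th percentile: neither is.

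**Step 3. Reproduce the plan's sample size.** Inputs from the sample size section: 15% versus 7%, type I error 5% (two-sided per the SAP), power 80%. With pooled proportion 0.11 and d = 0.08:

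- n = [1.960·√(2·0.11·0.89) + 0.842·√(0.15·0.85 + 0.07·0.93)]² / 0.08² = 238.9, i.e. 239 per arm.
- With continuity correction: (n/4)·[1 + √(1 + 4/(n·d))]² = 263.4, i.e. 264 per arm, which is the plan's figure.

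At the planned 270 per arm, power is 84.6% uncorrected. Corrected power uses the same formula at n₀ = (270 − 1/0.08)²/270 = 245.6 and is 81.1%.

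**Step 4. Illustrate the dilution under reading (a).** Two inputs are assumed because the documents do not give them: Holstebro's share of the trial, and the fraction f of its patients with a baseline between the two thresholds who become events without a 20% rise. With x = share × f, each arm's rate becomes p′ = p + x(1 − p). Power at 270 per arm, uncorrected / corrected:

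| Holstebro share | f = 5% | f = 10% | f = 20% |
|---|---|---|---|
| 10% | 83.0 / 79.3 | 81.3 / 77.5 | 78.0 / 74.0 |
| 20% | 81.3 / 77.5 | 78.0 / 74.0 | 71.7 / 67.4 |
| one third | 79.1 / 75.2 | 73.8 / 69.5 | 63.9 / 59.5 |

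The risk ratio moves from 0.47 (7/15) to between 0.48 and 0.64. For a one-third share and f = 10%, x = 0.0333, the rates are 17.8% and 10.1%, and expected events go from 40.5 versus 18.9 to about 48.2 versus 27.3. With a 10% share and f = 1%, power is 84.3 / 80.7, a loss of 0.3 points uncorrected.

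**Step 5. Allow a higher true rate at the lower cut-off.** Take a one-third Holstebro share and keep the risk ratio at 7/15. Uncorrected power:

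| Holstebro true control rate | f = 0 | f = 10% |
|---|---|---|
| 15% | 84.6 | 73.8 |
| 20% | 88.6 | 79.3 |
| 25% | 91.7 | 84.0 (corrected 80.9) |

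Within each assumed rate the unchanged values cost power. Against the planned power, the net direction is not known.

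**Step 6. Look for a backstop.** The protocol's Statistics section plans "a second analysis, which will only include patients with an ischemic disease", but the medical evaluation behind it is stated only for cTnI of at least 45 ng/L, so it does not reach the gap. The SAP stratifies by assay for peak and area under the curve only. The site-effect analysis may show heterogeneity but does not decide what counts as an event.

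**The case against.** The strongest reply is that reading (c) was probably meant. The Holstebro line sits under a parent bullet carrying the four-day window and the 20% rule, so it can be read as replacing the cut-off alone. Both cut-offs and the footnote carry the 99th percentile label. On that reading nothing is miscoded and the defect is a footnote that was not updated. This is plausible, but it is inference: the footnote's only number is 45, with the Vista assay's imprecision figure, while the infarction criterion was given an explicit Holstebro value.

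It is also fair that the power figures rest on assumed inputs and that the lowest ones need the top of both ranges together. That stands.

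A further point limits what the fix recovers. The protocol gives a 14% CV at the Holstebro cut-off. If that held at 30 ng/L (an assumption), the difference between two measurements would have an SD of about 0.14 × √2 = 20%, the same size as the required rise. Simulating a truly constant 30 ng/L, the aligned rule still codes 28% of patients as events with two postoperative samples and 38% with four. At a 10% CV the figures are 16% and 24%, and at 7% about 6% and 9 to 10%. As written, 99 to 100% are events in every case. The power differences above are therefore an upper bound on the gain.

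Lastly, a preoperative value in the gap is not itself an event: a patient whose later samples are all 24 ng/L or lower is not counted.

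**Conclusion.** The concern holds. As written, the primary outcome at Holstebro counts unchanged, and some falling, troponin values when the preoperative value is above 24 and below 45 ng/L, and does not count unchanged values of 45 ng/L or more. This is a stated rule that gives the wrong result, and no other current section corrects it.

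The expected effect is dilution, not bias: baseline precedes the intervention, so these events should be balanced between arms and type I error is unaffected. The primary outcome also differs by site for a reason beyond the assay.

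The textual defect is certain, but its size is not derivable from the documents. If the affected patients are 1% to 3.3% of the trial and the true rates are 15% and 7%, power at 270 per arm falls from 84.6% to between 81.3% and 73.8% uncorrected, or from 81.1% to between 77.5% and 69.5% corrected. With 0.1% affected the loss is negligible. It should be fixed because it concerns the primary outcome and the repair is cheap.

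**What to change.** Make footnote 1 site-specific: elevated at baseline means a preoperative value that meets the site's own event cut-off, ≥45 ng/L on the Dimension Vista and >24 ng/L on the Abbott assay. State in the Holstebro sub-bullet that the 20% rise requirement and the four-day window apply there too. Put the full event definition into the SAP's primary analysis, and settle it before allocation is unblinded.

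The cost is one sentence in each document. Preoperative troponin is already collected, so no new data are needed, and the planned 264 per arm does not change. The event count will be somewhat lower, and assay noise means that some truly unchanged patients will still be classified as events.

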**The PIXIE study**

**Statistical analysis plan for the primary publication**

**Definitions of the population**

*Intention-to-treat:* randomized in the trial and a minimum of two postoperative troponin assessments within four days of surgery (an evaluable primary outcome)

*Per-protocol:* randomized in the trial, received the allocated treatment, and a minimum of two postoperative troponin assessments within four days of surgery

We will do a per-protocol analysis and an intention-to-treat analysis.

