**Secondary analyses**

All analyses compare the difference between the intervention group and the control group. Continuous outcomes will be analyzed with non-parametric (Wilcoxon two-sample test) or parametric statistics (unpaired t-test) depending on data distribution and equality of variances. If necessary data will be logarithm transformed. Continuous outcomes will be expressed as mean (95% confidence interval) or median (inter-quartile range). Categorical outcomes will be analyzed with a chi-square test or Fischer's exact test (an expected count < five in one cell) and the result will be expressed as no. (%). Differences are considered significant if the two-sided p-value < 0.05.

Secondary comparisons include

- Peak plasma troponin I within four days of surgery (stratified on cardiac troponin I and high-sensitive troponin I)

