## **Final version**

- Total troponin I release (area under the curve) during the first four days after surgery (stratified on cardiac troponin I and high-sensitive troponin I)
- Perioperative myocardial infarction
- Major adverse cardiovascular events (30 days)
- Length of postoperative hospital stay
- Intensive care unit admission
- All-cause mortality (30 days)

To analyze the association between the intervention and the primary outcome, myocardial injury, we will do a univariate and multivariate logistic regression. The results will be expressed as odds ratios (95% confidence interval).

The decision to include a variable in the multivariate logistic regression will be based on clinical hypotheses. Trial site effect will be analyzed. A maximum of one variable per 10 primary events will be included.

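### NT-proBNP is measured before surgery and on day 1, but the plan does not say what is compared or how the preoperative value is used

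*Combined protocol and SAP*

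**What the plan says.** In the current (three-hospital) protocol, the secondary outcome list includes "Plasma N-terminal Pro-Brain Natriuretic Peptide (NT-proBNP) before surgery and at day 1 after surgery". The Participant timeline schedules the same two samples, and the Budget provides for 1080 analyses, which is 1080 / 540 = 2 per patient at the target of 2 x 270. Neither section names a summary measure.

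The protocol's Statistics section gives one general rule: "Data will be analyzed using non-parametric or parametric statistics depending on the distribution of data".

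The final SAP is more specific under Secondary analyses: "Continuous outcomes will be analyzed with non-parametric (Wilcoxon two-sample test) or parametric statistics (unpaired t-test) depending on data distribution and equality of variances". It allows log transformation where necessary and fixes the contrast: "All analyses compare the difference between the intervention group and the control group". It is titled "Statistical analysis plan for the primary publication", however, and NT-proBNP is not among its secondary comparisons. Its one regression serves the binary primary outcome: "To analyze the association between the intervention and the primary outcome, myocardial injury, we will do a univariate and multivariate logistic regression".

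**The concern.** Remote ischemic preconditioning starts after induction of anesthesia, so a preoperative NT-proBNP value cannot reflect the treatment. It tells us about the patient, not about the effect. The protocol nevertheless lists it as part of the outcome and gives it no role in the analysis.

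Two things follow. First, several analyses would fit the text. For the day-1 level there are three: t-test on the raw scale, t-test on the log scale, and Wilcoxon. For the change there are four: t-test or Wilcoxon, each on the raw difference or on the log ratio. That makes 3 + 4 = 7 analyses, and the choice among them could be made after the data are seen.

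Second, none of the seven removes the between-patient spread as well as regression on the baseline value does. Eligibility runs from age 45 upward, with or without heart failure, and excludes renal impairment only below an eGFR of 30. A wide spread in preoperative values is a reasonable expectation, although the documents give no SD. An effect on this marker could be estimated less precisely than the samples already taken would allow.

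**Working it through.** **The plan's own figure.** The documents give no SD, effect size or power for NT-proBNP. The only related figure is the trial's 264 per arm (15% versus 7%, two-sided 5%, power 80%).

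- Without continuity correction: n0 = [1.960 x sqrt(2 x 0.11 x 0.89) + 0.842 x sqrt(0.15 x 0.85 + 0.07 x 0.93)]^2 / 0.08^2 = 238.9, or 239.
- With correction: (n0/4) x [1 + sqrt(1 + 4/(n0 x 0.08))]^2 = 263.4, or 264.

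The stated figure reproduces, so the sample size is not in question.

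**Inputs for NT-proBNP.**

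- n = 270 per arm, the recruitment target. It is an upper bound here, because the protocol's Summary of Changes dates the NT-proBNP measurement to February 2015 at one site and January 2016 at another.
- Two-sided 5% level, from the SAP's Secondary analyses; power 80%, as in the sample-size section.
- r, the within-arm correlation between preoperative and day-1 log NT-proBNP. This is an assumption, shown from 0.3 to 0.85.
- Equal SDs (s) at the two time points, also an assumption. It matters only for the change score.

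**Variance of the treatment difference.**

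- Day-1 level only: 2s²/n
- Change score: (2s²/n) x (2 - 2r)
- Regression on baseline: (2s²/n) x (1 - r²), ignoring the small cost of estimating the slope

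The ratio of regression to day-1 only is therefore 1 - r². The ratio of regression to change score is (1 - r²)/(2 - 2r) = (1 + r)/2. The confidence interval narrows by 1 minus the square root of the ratio.

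| r | 1 - r² | CI narrower than day-1 only | (1 + r)/2 | CI narrower than change score |
|---|---|---|---|---|
| 0.3 | 0.91 | 5% | 0.65 | 19% |
| 0.5 | 0.75 | 13% | 0.75 | 13% |
| 0.7 | 0.51 | 29% | 0.85 | 8% |
| 0.85 | 0.2775 | 47% | 0.925 | 4% |

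**As detectable differences.** With 270 per arm and a day-1-only test, the difference detectable at 80% power is (1.960 + 0.842) x sqrt(2/270) = 0.241 SD. Multiplying by the square root of each variance factor gives:

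| r | Day-1 only | Change score | Regression on baseline |
|---|---|---|---|
| 0.3 | 0.241 SD | 0.285 SD | 0.230 SD |
| 0.5 | 0.241 SD | 0.241 SD | 0.209 SD |
| 0.7 | 0.241 SD | 0.187 SD | 0.172 SD |
| 0.85 | 0.241 SD | 0.132 SD | 0.127 SD |

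The change score beats the day-1 level only when r exceeds 0.5. Regression is at least as precise as either at every r, so the choice does not require knowing r in advance. Fewer than 270 patients per arm would enlarge every entry by the same factor and leave the percentages unchanged.

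**The case against.** A reader might infer that the plan discards the preoperative value and so gives away a large part of the precision. The documents do not support that.

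- The protocol's Statistics section is generic. Regression on a baseline value is itself a parametric method, and nothing in that section excludes it.
- Listing both time points under the outcome fits a change or ratio at least as well as a day-1-only comparison. A preoperative value can properly form part of a change score; it is not confined to the role of covariate.
- The SAP's silence follows from its scope. It also omits the endothelial and coagulation measures and the one- and five-year outcomes. Its two-sample tests were not written for NT-proBNP.
- A large loss needs both a high r and a day-1-only test. The documents give no r, and the Introduction describes drastic systemic changes around surgery, so a high r cannot be taken for granted. If the change were tested and r were high, the loss would be 4% to 8%.
- Adjustment is not wholly free. In emergent or urgent surgery some preoperative samples may be missing, and a complete-case regression would drop those patients.

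All of this stands, and it limits the point to a gap in specification and efficiency. The gap itself remains: the summary measure is undefined, and no baseline-adjusted analysis of this outcome is planned anywhere.

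**Conclusion.** The point holds as a minor one. The plan leaves the NT-proBNP comparison undefined, and the tests it names for continuous outcomes elsewhere are unadjusted. The precision at stake ranges from a few percent of the interval width to nearly half, depending on r and on which unadjusted test would have been used. Those figures rest on an assumed r and, for the change score, on equal SDs before and after surgery. Randomisation keeps any of the unadjusted comparisons unbiased, so validity is not at issue. The case for prespecifying the analysis does not depend on r.

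**What to change.** Add a short statement to the protocol's Statistics section, or to an analysis plan for the biomarker outcomes:

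- The outcome is day-1 NT-proBNP; the preoperative value is a baseline covariate.
- Log day-1 NT-proBNP is analysed by linear regression on treatment, log preoperative NT-proBNP and site.
- The result is reported as an adjusted ratio of geometric means with 95% CI.
- Missing preoperative values are handled by a simple stated rule, such as baseline mean imputation or a missing indicator, so that no randomised patient with a day-1 value is dropped.

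The cost is a few lines of text and no new samples. The SAP already permits log transformation and already plans a multivariable model and a look at trial site effect for the primary outcome, so nothing here is foreign to the plan. The statement should be dated before NT-proBNP results are seen by arm.
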